Protocol Title: Surgicel Snow in Gynecological Surgery

NCT number: NCT02908841

Version Date: 08/11/2016

Background:

Surgicel Snow is a topical hemostatic agent for use during surgical procedures. Topical hemostatic agents are classified into four categories based upon functional characteristics: mechanical agents, biological agents, flowable sealants, and fibrin sealants. The mechanical agents are further subcategorized by origin of component monomers including porcine gelatin, bovine collagen, oxidized regenerated cellulose, and polysaccharide spheres. The effectiveness, risk profile, and mechanism of action differ by hemostatic classification. Like the other mechanical agents, Surgicel Snow forms a physical barrier that blocks blood flow while providing a large surface area for the rapid formation of a fibrin clot. As a mechanical agent derived from oxidized regenerated cellulose, Surgicel Snow shares with other mechanical hemostatic agents, the benefits of a favorable risk profile. It is relatively inexpensive, rapidly absorbed (14 days), rarely induces a local inflammatory response or fibrosis, and no reported potential for inducing immunological response or anaphylaxis. A possible added benefit of oxidized regenerated cellulose topical hemostats is the antimicrobial effect of the lowered pH with the barrier layer (1). As is the case for all mechanical agents, the effectiveness of Surgicel Snow is limited by the need of an intact coagulation mechanism, as it will not enhance the rate of thrombus formation without adequate levels of coagulation factors. Surgicel Snow is generally used for minimal to mild bleeding from focal or widespread sources (2).

The use of oxidized regenerated cellulose has been shown to reduce length of stay and resource utilization in cardiovascular and neurosurgical procedures (3). With the exception of a small number of studies on myomectomy and conservative ovarian surgery (4-9), there is a paucity of evidence to support a benefit associated with the use of topical hemostats during gynecological surgery. Although it is known that all of the agents presently

approved by the FDA are capable of shortening the bleeding time associated with surgical incisions, there are no studies to show comparative efficacy or clinical impact with respect to estimated blood loss, transfusion rates or overall cost of care (10). Because of this lack of quality studies, there are few guidelines available for usage by clinical situation or by type of hemostatic agent. Notwithstanding the generally high level of confusion among gynecologic surgeons concerning indications for using topical hemostatic agents, it appears that these agents are being used with increasing frequency (11). The need for additional studies on the clinical impact of topical hemostatic agents during gynecologic surgery is clear.

The gynecologic procedures that provide the most interesting opportunities for clinical research on topical hemostatic agents at present are hysterectomy, resection of deeply infiltrating endometriosis, surgical management of active pelvic inflammatory disease, and sacrocolpopexy. These procedures share the requirement for dissection of the pelvic retroperitoneal spaces and are thereby associated with the risk of venous oozing adjacent to vital structures that limit the options for standard hemostatic methods. The retroperitoneal space of the pelvis (12) include the pararectal space, paravesical space, retropubic space, vesicovaginal space, rectovaginal space, and the presacral space (Triangle of Cote). The retroperitoneal spaces are potential spaces that are created by dissection to facilitate the identification, mobilization, and excision of pelvic retroperitoneal structures such as the ureters, iliac vessels, lymphatics, deeply invasive endometriosis, and residual ovaries. As the boundaries between structures of different embryological origins, the retroperitoneal spaces are generally avascular. These avascular planes are bordered by richly vascularized structures that can be easily disrupted by the dissection required to develop these space or by manipulation of the structures bordering these spaces. Bleeding

from the development of the pelvic retroperitoneal space is generally minimal and frequently, but not always, requires no specific hemostatic measures. Bleeding from mobilization or excision of retroperitoneal structures, such as during lymphadenectomy and dissection of cervical or intra-ligamental leiomyoma, has a greater propensity for blood loss and will frequently require standard hemostatic measures such as vascular clips, suture ligation, or electrosurgical methods for control. Although retroperitoneal bleeding occurs in a minority of the proposed procedures, the nature of bleeding within the retroperitoneal space is similar among the three procedures proposed.

The results of extensive bleeding in the retroperitoneal spaces include significant blood loss with dissection along the extraperitoneal fascial planes, as well as intraperitoneal collection, hematoma, and abscess. Patients with postoperative pelvic collections may present with symptoms of fever, rectal pain, or lower abdominal pain (13). Treatment often requires IR (interventional radiology) drainage and readmission for inpatient parenteral antibiotic therapy. The initial approach to hemostasis in the pelvis depends on the nature of bleeding encountered. When bleeding is encountered during pelvic dissection, evaluation of the extent and sources of bleeding, as well as its anatomic location and proximity to vital structures are the first requirements. The process of evaluating bleeding requires inspection of the bleeding sites augmented by irrigation, suctioning, and blotting with gauze. Through this process, the rate (minimal, mild, moderate, and severe)¹, distribution

¹ Estimated as blood loss in 10 second observation time as follows

1. minimal less than 2 cc
2. mild 2-3 cc
3. moderate 3-5 cc
4. severe ≥ 5

(local vs. diffuse), anatomic site (i.e., if in close proximity to vital structures), and source of blood loss (small arterial, venous or capillary) is ascertained.

Objectives:

This study would examine the efficacy of Surgicel Snow vs. direct compression in the control of capillary, venous, and small arterial hemorrhage when ligation or other conventional methods of control are impractical or ineffective in patients undergoing laparoscopic or robotic assisted laparoscopic hysterectomy. The intraoperative inclusion bleeding characteristics are minimal and mild retroperitoneal bleeding and moderate retroperitoneal bleeding that has been adequately reduced by standard surgical methods.

Design:

The proposed research method will use a randomized, concurrent control, no blinding. We are limiting our study to retroperitoneal dissection hysterectomy only to control for the expected variation in bleeding among the potential procedures. We propose to randomize 60 patients - 30 to the treatment group and 30 to the control group. The patients participating in this study would be patients scheduled for hysterectomy at Norwalk Hospital and Danbury Hospital under the direction of [name], [name], and [name].

The patient population is drawn from throughout the State of Connecticut. Indications for hysterectomy will include benign, complex benign uterine and adnexal pathology, as well as gynecologic oncology cases. Vaginal hysterectomy procedures and open abdominal procedures will be excluded. Complex benign pathologies are those that are likely to require retroperitoneal dissection and or ureterolysis, (e.g., cervical leiomyoma, endometriosis, etc.

Peritoneal access for hysterectomy will include open laparotomy, standard multiport laparoscopy, and robotic assisted laparoscopy. All patients scheduled for indicated procedures will be screened for inclusion. Once consented, patients will be randomized to the control group or the treatment group. The control group will receive standard of care, and the treatment group will receive Surgicel Snow. A random number generator will be used to determine test vs. control in blocks of 10.

For patients with qualifying bleeding (rated on initial evaluation as at least “mild”) who have been randomized to receive Surgicel Snow, a single thin layer of dry Surgicel Snow will be applied over the area of bleeding and positioned firmly in direct contact to the areas of bleeding with blunt surgical instruments. Surgicel Snow will be left in the cavity to be absorbed. Dry gauze will not be placed over the material. No adjuncts will be added to enhance hemostasis, but patients with small arteriolar bleeding will have pressure maintained on the bleeding site for 60 seconds. Control patients will be managed with direct compression with gauze pads or laparotomy pads for four minutes. If hemostasis is not achieved by compression after four minutes, the source and rate of bleeding will be reevaluated and management will be determined by the surgeon. If the surgeon uses Surgicel Snow to achieve hemostasis at some point after 4 minutes, the patient will be included in the control group, but his/her data will be and flagged for the analysis.

Hemostasis will be defined as the absence of free-flow bleeding, specified as no new appearance of blood from the bleeding site. Pinpoint or petechial bleeding that appears but does not grow, or saturation of blood into the hemostat that may have occurred prior to or during the application of hemostatic agent that did not spread during the observation period, will not be considered free-flow bleeding. Control and treatment patients who do

[figure not shown]
not require a topical agent to achieve hemostasis, thus not requiring a bleeding evaluation will be excluded from the study.

For control patients, hemostasis failures at 4 minutes will be managed as per judgment of the primary surgeon, most likely be the use of a topical sealant. For treatment patients, hemostatic failure at 4 minutes will be reassessed for rate of blood loss and if the rate of loss is estimated at less than 25 cc per minute, additional observations will be made at 7 and 10 minutes. If failure of hemostasis at 4 minutes with an estimated loss of ≥ 25 cc/min, patient will be managed as per judgment of surgeon. Persistent bleeding at the 10 minute observation point will be treated as per the surgeon's judgment. The nature of the bleeding will be recorded throughout the study.

Follow-up visits at 2 weeks (+/- 1 week) and 6 weeks (+/- 1 week) will be scheduled to determine if the patient has had a symptomatic collection or pelvic abscess. All subsequent procedures will be recorded, particularly those to manage bleeding.

The physician will take the time to describe the potential risks and benefits of the study as outlined in the consent form, to the patient. This will be reiterated by the assigned research coordinator. Only patients who have signed appropriate consent forms will be included in the study. Trained coordinators will be used and all standard safety protocols of the Clinical Research Department will be followed. The trained research coordinators will collect data at time of surgery. Should there be an adverse event, this will be documented and reported to the Principal Investigator (PI) and the IRB.

Intraoperative Flow Diagram

Selection and withdrawal of subjects:

Inclusion criteria:

1. Women ≥ 18 years of age
2. Women scheduled for standard multiport laparoscopic, single site laparoscopic, and robotic assisted laparoscopic hysterectomy.
2. Sites of surgery include Norwalk Hospital and Danbury Hospital.
3. Indication for surgery includes benign, complex benign, and malignant conditions.
4. Signed informed consent

Exclusion criteria:

1. Vaginal hysterectomy or open abdominal hysterectomy;
2. Congenital or acquired coagulation disorder including recent (within 7 days of surgery) therapeutic anticoagulation or use agents affecting platelet function, other than low dose aspirin. (Preoperative prophylactic heparin is not an exclusion criterion.)
3. Hysterectomy at the time of sacrocolpopexy.
4. Ovarian cancer

Participants may be withdrawn from the study at their request. Should a participant choose to withdraw from the study, no further clinical data will be collected on that patient and there will be no subsequent follow-up. In the event that a participant chooses to withdraw from the study, an additional study participant may be recruited to replace her.

Treatment of subjects:

Participants may continue all regular medications before and during the study.

The consent process will be incorporated into the consult visit prior to surgery.

Assessment of Efficacy:

The proposed clinical endpoints are time to hemostasis and failure to achieve hemostasis.

Because multiple factors other than retroperitoneal bleeding contribute to the total intraoperative blood loss, we believe that the intraoperative estimated blood loss is not a pure indicator of the efficacy of a topical hemostatic agent for control of retroperitoneal bleeding. The determination of the primary endpoint of time to hemostasis is based upon a modification of the methods used by Hutchinson, et al in Cellulose (15). Secondary endpoints will include total operative time, intraoperative blood loss, blood transfusion, postoperative hemoglobin decrease, rate of postoperative symptomatic fluid collection,

postoperative pelvic abscess, and total cost for care from day of operation until six week (+/- 1 week) postoperative visit.

Assessment of Safety:

Whereas Surgicel Snow is generally used for minimal to mild bleeding from focal or widespread sources, should there be an adverse event related to the study conduction, this will be documented and reported to the study's PI. The PI will evaluate whether the adverse event involves risk to participants or others. If so, the PI may choose to change the protocol, change the consent form, require that all participants already enrolled be notified and/or re-consented, or suspend or terminate the study.

Statistical Analysis:

All data will be collected in paper format and transferred to an electronic database where all PHI will be removed and replaced with a study number. After conducting descriptive analyses, we will compare the treatment and control group on the primary and secondary outcomes. Multivariate analyses will be used to control for any observed variation between the study groups. Statistical significance will be assessed at $p < 0.05$.

It is anticipated that 60 participants will be enrolled in this study. The study will be terminated once all patients have completed their 6 week (+/- 1 week) follow-up post-surgery.

Direct Access to Source Data Documents:

The study's data collection sheet outlines when each data point will be collected. The study's PI, primary study coordinator, and co-authors will have access to all study data. These data will be used for study purposes only, and will be stored on a password-

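### Blinding is ruled out without distinguishing roles, although the patient could cheaply be kept unaware of her arm; symptomatic fluid collection is therefore open to differential reporting

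*Combined protocol and SAP*

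**What the plan says.** The Design section sets out the method in one line: "The proposed research method will use a randomized, concurrent control, no blinding". Patient, surgeon and follow-up assessor are not distinguished, and no later section qualifies the statement.

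On timing, Design says "Once consented, patients will be randomized to the control group or the treatment group", and Treatment of subjects says "The consent process will be incorporated into the consult visit prior to surgery". The assignment can therefore exist before the patient reaches the operating room. On size: "We propose to randomize 60 patients - 30 to the treatment group and 30 to the control group".

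Both arms are delivered during the operation. The inclusion criteria name "Women scheduled for standard multiport laparoscopic, single site laparoscopic, and robotic assisted laparoscopic hysterectomy". Controls receive compression with pads. In the treatment arm, "Surgicel Snow will be left in the cavity to be absorbed".

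Follow-up visits at 2 and 6 weeks (each plus or minus 1 week) "will be scheduled to determine if the patient has had a symptomatic collection or pelvic abscess". The Background describes how such events come to notice: "Patients with postoperative pelvic collections may present with symptoms of fever, rectal pain, or lower abdominal pain". Assessment of Efficacy makes time to hemostasis the primary endpoint. Symptomatic fluid collection, pelvic abscess and total cost to the six-week visit are among the secondary endpoints, and Design adds that all subsequent procedures are recorded.

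The available text does not say whether patients are told their arm, who asks the follow-up questions, whether that person knows the arm, or what defines a symptomatic collection. It mentions no routine imaging. The consent pages are not part of the public text, so their absence is not counted against the plan.

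**The concern.** The surgeon cannot be blinded to whether a hemostat was applied. The patient is in a different position: she does not see the treatment given and is asked to do nothing that differs by arm. Leaving her unmasked appears to follow from a general statement about the trial, and no reason specific to her is given.

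This matters for an endpoint that becomes visible through complaints. A woman who knows she was assigned to a material left in her pelvis may report pain more readily, or seek care sooner, than a woman who knows she was assigned to compression. The opposite is also possible, so the direction of any bias cannot be predicted. A reported symptom can lead to work-up and to a diagnosis that would otherwise have gone unrecorded. With few events expected, a small difference in reporting could be a large part of the difference between the arms.

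**Working it through.** No figure in the protocol is in dispute. The only design figure is the sample size, and 30 + 30 = 60 is consistent. It cannot be reproduced as a powered size, because no effect size, standard deviation, event rate or power is given. The check is therefore which endpoints patient knowledge could reach, and how large the effect might be.

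**Which endpoints are exposed**

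- *Time to hemostasis (primary):* observed during the operation. Patient knowledge cannot affect it.
- *Symptomatic collection:* directly exposed. Of the three presenting symptoms in the Background, rectal pain and lower abdominal pain are patient-reported; fever is measurable.
- *Abscess, later procedures, cost:* indirectly exposed. They pass through clinical decisions such as drainage and readmission, and cost starts on the day of operation, so it includes the surgery itself.
- *Hemoglobin decrease:* a laboratory value, not open to reporting.

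**Size of one case**

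With 30 per arm, one extra diagnosis moves an arm's rate by 1/30 = 3.3 percentage points. If the true rate were 3% to 10% (an assumption), an arm would expect 30 × 0.03 = 0.9 to 30 × 0.10 = 3 events. One extra case on 1 event is a relative change of 1/1 = 100%; on 3 events it is 1/3 = 33%. If exclusions after randomization leave fewer than 30 evaluable patients in an arm, the step is larger.

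**Effect of unequal reporting**

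Suppose the true collection rate *p* is the same in both arms, but 60% of events come to notice in one arm and 100% in the other. This is a deliberately severe assumption. The spurious difference is *p* × (1.00 − 0.60), and the expected observed events are 30 × *p* × 0.60 and 30 × *p* × 1.00. The last column is the probability that a two-sided Fisher exact test at 0.05 rejects, summed over all binomial outcomes. The protocol sets p < 0.05 but names no test and no sidedness, so the test is also an assumption.

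| Assumed true rate | Spurious difference (points) | Expected events observed | P(reject) |
|---|---|---|---|
| 3% | 1.2 | 0.5 vs 0.9 | 0.0001 |
| 5% | 2.0 | 0.9 vs 1.5 | 0.0014 |
| 10% | 4.0 | 1.8 vs 3.0 | 0.015 |
| 20% | 8.0 | 3.6 vs 6.0 | 0.065 |

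With a milder imbalance of 70% vs 90%, the rejection probabilities are 0.0001, 0.0008, 0.0079 and 0.029. With equal 70% reporting they are at most 0.016.

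The reason they are low is that, with zero events in one arm, the other needs at least 6 for significance. For 0 vs 5, p = 2 × C(30,5)/C(60,5) = 2 × 142,506/5,461,512 = 0.052. For 0 vs 6, p = 2 × C(30,6)/C(60,6) = 2 × 593,775/50,063,860 = 0.024.

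**The case against.** The other side has a good deal to say.

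- The plan openly declares an unblinded design and does not contradict itself here. That stands: this is an improvement to a design choice, not the correction of an error.
- Unblinded does not mean that patients are told. A reader might infer that they are, but the documents do not say so, and the consent pages might settle it. That stands; the point is only that nothing in the available text prevents it.
- Anesthesia is never mentioned. True, but it follows safely from laparoscopic or robotic hysterectomy.
- A reader might picture patients who know material was left against patients who know none was. Design blurs this: control failures at four minutes go to the surgeon's judgment, most likely a topical sealant, and controls given Surgicel Snow stay in their group and are flagged. A control patient cannot be sure that nothing was left. This weakens the contrast without removing it.
- A reader might take the follow-up measures to be the trial's only postoperative safety outcomes. They are not. Adverse events are documented and reported, and transfusion and hemoglobin decrease are secondary endpoints.
- A reader might suppose that the bias could be removed at no cost. It could only be reduced. The surgeon stays unblinded, and a form that hides the arm does not mask whoever orders imaging or readmits the patient.
- Unblinded judgment of hemostasis in the operating room bears on the primary endpoint and matters more. Agreed, but it is a separate matter and no reason to leave this one as it is.

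**Conclusion.** The point holds in a limited form and is minor. Blinding is ruled out without limit by role, and the order of consent and randomization allows a patient to learn her arm before surgery. One secondary endpoint, symptomatic fluid collection, is directly open to differential reporting as a result.

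The likely harm is a biased rate, not a false claim of significance. Under the severe 60% vs 100% assumption, the spurious difference is 1.2 to 4 points at true rates of 3% to 10%, with a rejection probability of no more than 0.015. Even at a 20% rate it is 0.065. Since the counts will be small, readers will look at the rates themselves, and there a single case counts.

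All event rates and reporting levels here are assumptions. The documents support no estimate of the actual size or direction of the bias. Confidence that it would matter in practice is low, and no change in sample size follows.

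**What to change.** In Design, replace the general statement with one that names roles, for example: *The surgeon is not blinded. The patient is not told her assignment until after the six-week visit, except on request or for clinical need.* Ask the symptom questions at 2 and 6 weeks from a standard form that does not show the arm. At six weeks, also ask each patient which arm she believes she was in, and report the answers by arm so that readers can judge how well the masking held.

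The cost is a change to the consent and form wording and one extra question. Neither treatment nor the visit schedule changes. The downside is that masking will be incomplete: some patients may learn their arm from the operative record or from the unblinded surgeon.

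### The Objectives admit minimal bleeding, but the Design qualifies only bleeding rated at least mild and states that floor only for the Surgicel Snow arm; one complete rule for both arms is needed.

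*Combined protocol and SAP*

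**What the plan says.** The Objectives state: "The intraoperative inclusion bleeding characteristics are minimal and mild retroperitoneal bleeding and moderate retroperitoneal bleeding that has been adequately reduced by standard surgical methods". Footnote 1 in the Background gives the scale as estimated loss over 10 seconds: "minimal less than 2 cc", mild 2 to 3 cc, moderate 3 to 5 cc, severe 5 cc or more.

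The Design gives a different threshold in its instructions for the Surgicel Snow arm: "For patients with qualifying bleeding (rated on initial evaluation as at least" mild, continuing "who have been randomized to receive Surgicel Snow, a single thin layer of dry Surgicel Snow will be applied over the area of bleeding". The control instruction comes later in the same paragraph and mentions neither a grade nor qualifying bleeding: "Control patients will be managed with direct compression with gauze pads or laparotomy pads for four minutes".

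The one exclusion written for both arms turns on need, not grade. It removes patients who do "not require a topical agent to achieve hemostasis, thus not requiring a bleeding evaluation will be excluded from the study". The criteria under Selection and withdrawal of subjects contain no bleeding grade. The intraoperative flow diagram is not reproduced in the text available for review.

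The Design also says that patients are randomised once consented and that there is no blinding. The primary endpoint is time to hemostasis.

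**The concern.** The bleeding grade decides which randomised patients enter the primary comparison, and two written rules give opposite answers for the lowest grade. The arm is assigned at consent, the grade is estimated during surgery, and the surgeon knows the arm when grading. Where the rules disagree, either choice can be defended from the text, and the choice is made with the allocation known.

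Grade probably matters for the outcome, since lighter bleeding can be expected to stop sooner under either method. If minimal bleeds entered more often in one arm, that arm would look better without any true effect. Even if the floor is applied equally, the choice of rule changes the population and the number analysed.

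The Statistical Analysis section plans multivariate analyses for observed differences between the groups but does not name initial grade. Such adjustment can work only on patients who entered; it cannot recover those left out.

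**Working it through.** The plan gives no effect size, standard deviation or power for its 60 patients, so there is no figure to reproduce. The check is a comparison of the rules, grade by grade.

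| Grade at initial evaluation (loss in 10 s) | Objectives | Design wording | Selection criteria |
|---|---|---|---|
| Minimal, under 2 cc | in | out | silent |
| Mild, 2–3 cc | in | in | silent |
| Moderate, 3–5 cc, adequately reduced | in | in | silent |
| Moderate, not reduced | not listed | not ruled out | silent |
| Severe, 5 cc or more | not listed | not ruled out | silent |

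1. **Upper end.** The two texts can be read together, with the Objectives supplying the ceiling that the Design sentence lacks. The Design sentence is still not a complete rule on its own.

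2. **Lower end.** The texts cannot both be followed. They would agree if minimal in the Objectives meant the grade left after standard measures, but the Objectives attach reduction to moderate bleeding and list minimal separately.

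3. **How many patients are affected.** Only minimal bleeds that get an evaluation are in dispute, because patients needing no topical agent leave the study in both arms. That group need not be empty. The Background says bleeding from developing these spaces is "generally minimal and frequently, but not always, requires no specific hemostatic measures", and Assessment of Safety begins "Whereas Surgicel Snow is generally used for minimal to mild bleeding from focal or widespread sources". The documents give no share.

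4. **Form of the bias if the floor were applied in one arm only.** Let *m* be the share of minimal bleeds among evaluated bleeds, and *D* the amount, in SD units, by which their mean time is shorter. Assume no true effect. With the floor in the Surgicel Snow arm only, that arm has mean μ, and the control arm has mean (1 − m)μ + m(μ − D) = μ − mD. The spurious difference is *mD*, in favour of control.

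Neither *m* nor *D* is in the documents. Purely as an illustration, assume *m* of 20% to 40% and *D* of 0.5 to 1:

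- 0.2 × 0.5 = 0.10 SD; 0.2 × 1 = 0.20 SD
- 0.4 × 0.5 = 0.20 SD; 0.4 × 1 = 0.40 SD

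These values show scale only. The Design names assessments at 4 minutes in both arms, and at 7 and 10 minutes for Surgicel Snow. Part of any imbalance might therefore appear as more patients with hemostasis at 4 minutes rather than as a shift in mean time.

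**The case against.** **The floor is meant for both arms.** Qualifying bleeding reads like a trial-level term, the control instruction sits in the same paragraph, and the need-based exclusion names both arms together. The flow diagram may show a common evaluation step. This largely stands. A reader might infer that the plan sets different eligibility for the two arms by design, but the documents do not support that: they show where the floor is written, not that controls are exempt. The diagram cannot settle the lower limit without a text change, however, because if it sets a floor it can match only one of the two texts.

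**The two texts refer to different time points.** The Design speaks of the initial evaluation, while the Objectives include moderate bleeding as it stands after standard measures. This is arguable, but it requires extending the reduction clause to a grade the sentence lists without it.

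**Few patients are affected.** The Background remark that minimal bleeding often needs no measures also implies that many such patients never reach the disputed rule. This stands, and it limits the point to evaluated minimal bleeds.

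**Power or error rates cannot be derived.** A reader might go on to quote a loss of power or an inflated error rate based on 30 patients per arm. The documents do not support this. The Background says retroperitoneal bleeding occurs in a minority of the procedures, and patients without need are excluded after randomisation, so the number evaluable is unknown and may be well below 30 per arm.

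**Dropping minimal bleeds is a matter of preference.** The protocol describes the product as generally used for minimal to mild bleeding, so a floor at mild leaves out part of that use. This stands, and the choice belongs to the sponsor.

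**Conclusion.** The conflict at the lower limit is in the text: an evaluated bleed under 2 cc in 10 seconds is eligible under the Objectives and not under the Design, and the selection criteria do not resolve it. The single-arm wording is probably a drafting slip. It still deserves correction, because grading follows randomisation and the trial is open.

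Unequal application could bias time to hemostasis, but the size cannot be computed from the documents. The 0.10 to 0.40 SD range rests entirely on assumed values and on complete application of the floor in one arm. It is not an estimate for this trial, and the documents do not show that the comparison is in fact biased. This is a correction that should be made, at little cost; it is not a fatal flaw.

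**What to change.** Write one complete intraoperative eligibility rule, explicitly for both arms and with both limits. Use the same words in the Objectives, the Design and the selection criteria, and make the flow diagram match. One form is:

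*In either arm, bleeding qualifies if rated mild on initial evaluation, or if moderate and adequately reduced with standard surgical measures. Severe bleeding and moderate bleeding not so reduced do not qualify.*

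If the sponsor wants minimal bleeds that need a topical agent, add minimal to this rule in all three places and delete the at-least-mild condition from the Design.

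Under either choice:

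- record the initial grade, before treatment, for every evaluated bleed;
- report by arm how many randomised patients were excluded for grade;
- name initial grade as an adjustment variable in the primary comparison.

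The cost is wording in three places plus the diagram. The grade may already be collected, since the Design records the nature of the bleeding throughout. A floor at mild may reduce the number analysable and call for more enrolment, by an amount the documents do not allow to be calculated. Including minimal bleeds may dilute the difference if they benefit less. Neither choice removes the risk from grading with the arm known; reporting exclusions by arm only makes it visible.
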